8.1.5.2. Disease Characteristics and Treatment History

A disease-targeted medical and treatment history will be collected at screening. Details regarding the participant's history of SS, including date of diagnosis, relevant disease characteristics, and prior treatments (including systemic treatments, radiation, and surgical procedures), will be recorded. A medical history of other conditions related to SS will also be collected at this time.

8.2. Efficacy Assessments

8.2.1. Ultrasound of Salivary Glands

Ultrasound measurement of the parotid and submandibular glands will be performed at visits indicated in [Table 3](#). Ultrasound of glands will be performed in the longitudinal and transverse planes with participants in a supine position. The ultrasound images will be images will be evaluated for quality then transmitted to a central vendor for reading and data summarization. The echostructure of each gland on B-mode images will be graded on a 5-point scales (0 to 4) as described by [Gazeau et al 2018](#). Grade 0 indicates a normal homogeneous gland, Grade 1 small hypoechoic areas with hyperechoic bands, Grade 2 multiple hypoechoic areas less than 2 mm, Grade 3 multiple hypoechoic areas 2 to 6 mm, and Grade 4 multiple hypoechoic areas larger than 6 mm. For each participant at each timepoint, 4 grades will be obtained, one for each parotid and submandibular gland. The SGUS score is the numeric sum of the 4 individual grades. [REDACTED]

[REDACTED] Instructions for conducting and transmitting ultrasound measurements will be provided in the Study Manual.

8.2.2. EULAR Sjögren's Syndrome Disease Activity Index

Investigators will conduct overall disease assessment using the ESSDAI ([Seror et al 2015](#)) at visits indicated in [Table 3](#). The ESSDAI assesses 12 domains: constitutional, lymphadenopathy/lymphoma, glandular, articular, cutaneous, pulmonary, renal, muscular, peripheral neuropathy, central nervous system, hematologic, and biologic. Guidance for completing the assessment will be provided in the Study Manual.

8.2.3. Salivary Flow

Stimulated and unstimulated salivary flow will be measured at visits as indicated in [Table 3](#). Complete details for the collection and measurement of unstimulated salivary flow will be provided in the Study Manual.

8.2.4. Patient-Reported Outcomes

Patient-reported outcome instruments will be given to participants for completion at study visits indicated in [Table 3](#). Site staff will enter completed questionnaires into the eCRF database.

8.2.4.1. Dryness Questionnaire

The dryness questionnaire will ask participants to rate the dryness of eyes, mouth, or vagina (female participants only) with 24-hour recall using an 11-point numerical rating system ranging from 0 (no dryness) to 10 (worst imaginable; see [Appendix B](#)).

8.2.4.2. EULAR Sjögren's Syndrome Patient Reported Index

The ESSPRI consists of 3 items, each with a 0 (no symptom) to 10 (maximum imaginable symptom) scale. The 3 items are dryness, fatigue, and pain. The recall period is 2 weeks.

8.2.4.3. Patient Global Impression of Change Questionnaire

The PGIC asks a single question regarding how the patient is feeling since beginning new therapy. The questionnaire uses a 7 point scale ranging from "very much worse" to "very much improved," with the midpoint as no change.

8.2.4.4. Female Sexual Function Index

The FSFI is a brief, self-report measure of female sexual function (female participants only). The questionnaire contains 19 items covering 6 domains of sexual function. The recall period is 4 weeks.

8.2.4.5. PROMIS Fatigue Short Form

The PROMIS fatigue short form includes 7 items with a rating scale of 1 to 5. The recall period is 7 days.

8.2.4.6. European Quality Of Life 5 Dimensions Questionnaire

The EQ-5D is a standardized measure of health status. It consists of 5 questions, each with a 5-item rating scale plus a visual analog scale rating from 1 to 100 for overall health status. The questionnaire probes the participants responses for the current day.

8.2.5. Health Economics

Not applicable.

8.3. Safety Assessments

Planned timepoints for all safety assessments are provided in [Table 3](#).

See Section [6.5](#) for guidelines regarding the management of relevant laboratory or other safety assessment abnormalities.

8.3.1. Adverse Events

Adverse events will be monitored from the time the participant signs the ICF until at least 30 days after the last dose of study drug. Adverse events that begin or worsen after informed consent should be recorded on the Adverse Events Form in the eCRF regardless of the assumption of a causal relationship with the study drug. Conditions that were already present at the time of informed consent should be recorded on the Medical History Form in the eCRF. Adverse events (including laboratory abnormalities that constitute AEs) should be described using a diagnosis whenever possible rather than by individual underlying signs and symptoms.

Adverse events will be reported by the participant (or, when appropriate, by a caregiver, surrogate, or the participant's legally authorized representative). The investigator and any qualified designees are responsible for detecting, documenting, and recording events that meet the definition of an AE or SAE and remain responsible for following-up on AEs that are serious, considered related to the study treatment/procedures, or that caused the participant to discontinue the study drug. Care will be taken not to introduce bias when detecting AEs and/or SAEs. Open-ended and nonleading verbal questioning of the participant, such as "How are you feeling?" is the preferred method to inquire about AE occurrences. Adverse events may also be detected when they are volunteered by the participant during the screening process or between visits, or through physical examinations, laboratory tests, or other assessments. The definition, reporting, and recording requirements for AEs are described in Section 9.

All SAEs will be recorded and reported to the sponsor or designee within 24 hours. The investigator will submit any updated SAE data to the sponsor within 24 hours of it being available.

After the initial AE/SAE report, the investigator is required to proactively follow each participant at subsequent visits/contacts. All SAEs will be followed until resolution, stabilization, the event is otherwise explained, or the participant is lost to follow-up (as defined in Section 7.3).

8.3.2. Physical Examinations

Physical examinations will be conducted at the timepoints listed in Table 3.

A comprehensive physical examination will include height and body weight and assessment of the following organ or body systems: skin; head, eyes, ears, nose, and throat; thyroid; lungs; cardiovascular system; abdomen (liver, spleen); extremities; and lymph nodes. A brief neurological examination will also be performed.

A targeted physical examination should be conducted as indicated by symptoms reported by the participant, AEs, or other findings. Abnormalities that are considered clinically significant in the judgment of the investigator are to be reported as AEs.

Physical examinations must be performed by a medically qualified individual such as a licensed physician, physician's assistant, or an advanced registered nurse practitioner, as local law permits.

8.3.3. Vital Signs

Vital sign measurements (to be taken before blood collection for laboratory tests) include blood pressure, pulse, respiratory rate, and oral body temperature. Blood pressure and pulse will be

taken with the participant in the sitting position after 5 minutes of rest. Abnormal vital sign results identified after the first dose of study treatment constitute an AE if they are considered clinically meaningful, induce clinical signs or symptoms, or require concomitant therapy.

8.3.4. Electrocardiograms

Single 12-lead ECGs will be obtained as outlined in the SoA (see [Table 3](#)) using an ECG machine that automatically calculates the heart rate and measures PR, QRS, QT, and QTc intervals. All 12-lead ECGs will be performed as indicated in [Table 9](#) with the participant in a recumbent or semirecumbent position after 5 minutes of rest.

The 12-lead ECGs will be interpreted by the investigator at the site to be used for immediate participant management and care. Additional 12-lead ECGs may be performed as clinically indicated to manage participant safety. The decision to include or exclude a participant or withdraw a participant from the study treatment based on an ECG flagged as "Abnormal, Clinically Significant" is the responsibility of the investigator, in consultation with the sponsor's medical monitor, as appropriate. Clinically notable abnormalities that are considered clinically significant in the judgment of the investigator are to be reported as AEs.

Table 9: Electrocardiogram Schedule

Study Visit	Timing of Electrocardiogram Relative to Administration of Study Drug		
	Not Applicable	Predose (Trough) ECG	Postdose ECG
Screening ^a	Single → Triple ^b		
Day 1 ^c		Triple	Single → Triple ^b
Week 2 ^c		Single → Triple ^b	Single → Triple ^b
Week 12 ^d			Single → Triple ^b

^a Prolonged QTcF values (> 470 milliseconds for males or > 480 milliseconds for females) at screening are to be confirmed by performing 2 additional ECGs and averaging the results to determine whether the averaged value meets the exclusion criterion.

^b Single → Triple: Single ECG will be performed first. If prolonged QTcF intervals (defined as > 470 milliseconds for males or > 480 milliseconds for females) are observed, an additional 2 ECGs will be measured within the next 5 minutes.

^c Day 1 and Week 2 postdose ECGs will be performed after participants complete all of the study assessments [REDACTED]

^d Week 12 postdose ECGs will be performed after participants complete all of the study assessments.

All ECG measurements should be performed before blood draws for laboratory [REDACTED] assessments, and all predose (trough) ECG measurements should be taken before the participant takes study drug for that day.

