This is an open-label, Phase 2 study to assess the impact of PI3K δ inhibitor INCB050465 on signs and symptoms of SS. A single group of 12 participating adults, \geq 18 years old, who meet the inclusion criteria, will be enrolled for a duration of 12 weeks (with a 30-day safety follow-up period) and receive treatment with INCB050465 1.0 mg QD. Participants will undergo ultrasound measurement of salivary glands, measurements of salivary flow, collection of symptom questionnaires, and PD [REDACTED] blood sampling to allow studies of cytokine levels, gene expression levels, and other PD markers.

The study design is shown in [Figure 1](#).

Adherence to the study design requirements, including those specified in the SoA, is essential and required for study conduct.

[Table 3](#) provides the SoA for the study, and [Table 4](#) provides a Schedule of Laboratory Assessments.

Table 3: Schedule of Activities

	Screening (Day -28 to Day -1)	Day 1	Week 2 (± 3 Days)	Week 4 (± 7 Days)	Week 8 (± 7 Days)	Week 12/ EOT (± 7 Days)	Safety Follow-Up (30 Days [+7 Days] After Last Dose of Study Drug)	Comments
Administrative Procedures								
Informed consent	X							
Contact IRT	X	X	X	X	X	X		
Inclusion/exclusion criteria	X	X						
Medical and medication history	X							
Concomitant medications	X	X	X	X	X	X	X	
Dispense reminder card		X	X	X	X			
Administer study drug during visit		X	X	X	X			
Dispense study drug		X	X	X	X			
Drug accountability and compliance assessment			X	X	X	X		
Administer PJP prophylaxis if needed*		X	X	X	X	X	X	From Day 1 to at least 30 days after last dose of study drug. *See Section 6.6.1.1.
Safety Assessments								
AE assessment	X	X	X	X	X	X	X	
Comprehensive physical examination	X						X	
Targeted physical examination		X	X	X	X	X		Body systems with symptoms should be physically examined.
Vital signs	X	X	X	X	X	X	X	Measure height at screening only.
12-lead ECG	X	X	X			X	X*	*Standard ECG.
Efficacy Assessments								
Ultrasound of parotid and submandibular salivary glands		X*		X		X		*Schedule ultrasound 2 weeks before Day 1 to ensure results availability.
Measurement of total unstimulated salivary flow	X	X		X	X	X		
Measurement of total stimulated salivary flow	X*	X		X	X	X		*Documented measurement within 12 weeks before screening visit.
Questionnaire for dryness of eyes, mouth, and (females only) vagina	X	X		X	X	X		
ESSDAI assessment	X	X		X	X	X		
ESSPRI questionnaire	X	X		X	X	X		
PGIC questionnaire	X	X		X	X	X		

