6.4. Study Treatment Compliance

Compliance with study drug should be emphasized to the participant by the site personnel, and appropriate steps should be taken to optimize compliance during the study. Compliance with INCB050465 will be calculated by the sponsor based on the drug accountability documented by the site staff and monitored by the sponsor/designee (tablet counts). Participants will be instructed to bring all study drug with them to the study visits in order for site personnel to conduct tablet counts to assess study drug accountability. The drug accountability documentation will be used by the sponsor to calculate treatment compliance.

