8.1.4. Distribution of Reminder Cards and/or Diaries

Participants will be provided with a reminder card on Day 1 and Weeks 2, 4, and 8. The reminder card will indicate the date/time of the next visit and will also remind the participant that they should not take their morning dose of study drug on the day of each study visit as they will take it after blood draws for safety evaluation have been completed. The reminder cards for each visit will have an area on which the date and time of the last dose taken (from the previous evening) and the time of their last meal before the visit should be recorded.

Participants will also be provided with a diary on Day 1 in order to record study drug administration daily. The date and time of the last dose of study drug [REDACTED] [REDACTED] will be recorded in the diary and eCRF. Daily study drug administration (see Section [6.1](#)) will also be recorded in the diary.

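### The only Week 12 ECG must be postdose, but Table 3 schedules no dose at that visit; separately, the rule that all ECGs precede blood draws conflicts, as printed, with every postdose ECG

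*Protocol*

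**What the plan says.** **ECG timing.** Protocol Section 8.3.4 states "Single 12-lead ECGs will be obtained as outlined in the SoA" and sends the reader to Table 9 for timing relative to the dose. Table 9 asks for predose and postdose ECGs at Day 1 and Week 2. At Week 12 only the postdose column is filled, and footnote d reads "Week 12 postdose ECGs will be performed after participants complete all of the study assessments". Footnote c, partly blacked out, puts the Day 1 and Week 2 postdose ECGs after all assessments too. The section's closing sentence, also partly blacked out, puts every ECG ahead of the laboratory blood draws.

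**Dosing on visit days.** Table 3 has a row "Administer study drug during visit", marked at Day 1 and Weeks 2, 4 and 8 and blank at Week 12/EOT. The 12-lead ECG row is marked at Week 12/EOT. Section 1 says of the schedule: "Adherence to the study design requirements, including those specified in the SoA, is essential and required for study conduct".

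**What participants are told.** Under Section 8.1.4 the reminder card tells participants that "they should not take their morning dose of study drug on the day of each study visit", and the sentence goes on: "each study visit as they will take it after blood draws for safety evaluation have been completed". Cards are given at Day 1 and Weeks 2, 4 and 8, and "The reminder card will indicate the date/time of the next visit". The Week 8 card therefore governs Week 12.

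**The concern.** Two instructions bear on whether a participant has taken drug before the Week 12 ECG, and they disagree. The Week 8 card tells the participant to arrive undosed because the tablet will be taken at the visit. The Table 3 dosing row shows no tablet at that visit. If the participant follows the card and the site follows the row, the ECG is recorded with no dose that day although the protocol calls it postdose.

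ECGs belong to the secondary safety endpoint (Protocol Table 5), and Week 12 is the last scheduled ECG on treatment. A participant caught by this conflict would have no scheduled postdose ECG after Week 2, and a predose reading would sit under a postdose label.

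The blood-draw sentence adds a problem of sequence. Even with a dose given at Week 12, a site that applies the sentence literally would record the ECG before the bloods, and so before the dose.

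**Working it through.** No figure in the plan bears on this point. The one stated design figure, a better than 90% chance of seeing at least one AE of interest at a 20% rate, reproduces as 1 − 0.8^12 = 0.931 and does not enter the argument.

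**Step 1: Table 3 beside Table 9.**

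| Visit | In-visit dose (Table 3) | Predose ECG (Table 9) | Postdose ECG (Table 9) |
|---|---|---|---|
| Day 1 | marked | yes | yes |
| Week 2 | marked | yes | yes |
| Week 4 | marked | none | none |
| Week 8 | marked | none | none |
| Week 12/EOT | blank | none | yes |

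Week 12 is the only visit with a postdose ECG and no dose marked. The blank does not look like a text-extraction fault: the dosing row has the same pattern as the rows for dispensing drug and reminder cards, and the ECG row lines up with the same column headers.

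**Step 2: readings exposed to the missing dose.** Planned postdose readings, counting a triplicate as one, are 3 visits × 12 participants = 36. Those at Week 12 are 1 × 12 = 12, or 12/36 = one third. This is a ceiling. It assumes that all 12 participants reach Week 12 on treatment, that all hold the morning dose, and that every site reads the blank cell as no dose.

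**Step 3: order of events.** Write A < B for A before B.

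- Section 8.3.4, last sentence: ECG < blood draws.
- Section 8.1.4: safety blood draws < dose.
- Together: ECG < dose, so the ECG is predose.
- Table 9, postdose column: dose < ECG.

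These cannot all hold. Footnotes c and d contradict the last sentence of 8.3.4 even without Section 8.1.4, because an ECG done after all assessments comes after the blood draws. The clash therefore covers Day 1, Week 2 and Week 12.

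**Step 4: an order that works.** If the before-blood-draw rule applied to predose ECGs only, the sequence predose ECG < blood draws < dose < remaining assessments < postdose ECG would satisfy Table 9, its footnotes and Section 8.1.4 at Day 1 and Week 2. Without the first item it works at Week 12, provided a dose is given.

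**Step 5: drug supply.** Taking Week 8 as Day 56 and Week 12 as Day 84, each ± 7 days, the longest interval the last supply must span is (84 + 7) − (56 − 7) = 42 days, against 84 − 56 = 28 days nominally.

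**The case against.** The strongest reply is that the protocol already answers the question. Table 9 exists to fix ECG timing relative to dose, and Section 8.1.4 promises a dose at each visit. Dosing is daily, and under Section 6.4 "Participants will be instructed to bring all study drug with them to the study visits". A site would have to put an empty cell above two explicit instructions. This largely stands. It makes the Table 3 cell the outlier and keeps the likelihood of harm low. It does not remove the conflict, because Section 1 makes the schedule binding and no text says which source prevails.

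The blank may also be deliberate. The column serves early-termination visits as well as Week 12, and an unqualified mark would tell sites to dose people who have stopped the drug. That also stands, and it shapes the fix. It does not explain how a postdose ECG is obtained from someone still on treatment.

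Redaction limits certainty. Section 8.4 is not visible, and both footnote c and the blood-draw sentence are cut. The hidden text may settle the order, so this point rests on the words as printed.

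Four stronger readings are tempting and are not supported:

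- **The Week 12 ECGs will be undosed, or QTc results will be biased.** The documents support only that a dose may be omitted. How many sites would omit it is unknown. A trough ECG under daily dosing is still an on-treatment reading.
- **The long interval since the Week 2 ECG measures the harm.** The interval is 84 − 14 = 70 days (60 to 80 within the windows), but it is built into the schedule and exists whether or not a dose is given.
- **Day 1 and Week 2 are untouched.** The blood-draw sentence covers all ECGs, so as printed it reaches those visits too.
- **All 36 postdose readings are compromised.** At Day 1 and Week 2 a dose is marked, Table 9 asks for separate predose and postdose recordings, and footnote c puts the latter last. The intended order is clear enough there, although the wording needs repair.

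**Conclusion.** The inconsistency is real and minor. For participants still on treatment, the protocol calls for a postdose ECG at Week 12, tells them to arrive undosed, and omits the dose from the schedule. The before-blood-draw sentence separately contradicts the postdose ECGs at all three visits as printed.

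The consequence is confined to the dose-timing label of one descriptive safety timepoint, at most 12 readings. Protocol Section 10.3 sets no formal efficacy hypothesis, and SAP Section 8.5 plans only descriptive ECG summaries and listings. No efficacy result or stated figure depends on it. Section 8.1.4 has last-dose times recorded in the diary and eCRF, so an undosed Week 12 reading could probably be identified afterwards, though the missing postdose reading could not be recovered. SAP Section 8.5 mentions no check of dose status; the table shells are in a separate document and were not available.

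This rests on two assumptions: that the blank cell is as the sponsor printed it, and that no blacked-out text already fixes the Week 12 dose or the order of ECG and blood draws.

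**What to change.** Three small edits and one check:

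1. In Table 3, mark in-visit dosing at Week 12/EOT, with a footnote limiting it to participants still on treatment and stating that no dose is given at an early-termination EOT visit.
2. In Section 8.3.4, limit the before-blood-draw rule to predose ECGs, so that postdose ECGs follow the dose and the remaining assessments as footnotes c and d require.
3. State whether daily dosing continues to the visit when Week 12 falls after Day 84.
4. Check that the Week 8 supply covers the visit day at the end of the +7-day window.

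Marking the Table 3 cell alone would not be enough, because the blood-draw sentence would still put the ECG ahead of the dose. Relabelling the Week 12 ECG as trough would also remove the contradiction, but it would give up the only postdose reading after Week 2 and would mean changing Table 9 and footnote d.

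The cost is a short protocol clarification, a note to sites and possibly a few extra tablets at Week 8. No procedure is added and no planned analysis changes.

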8.3.5. Laboratory Assessments

See [Table 10](#) for the list of clinical laboratory tests to be performed and the Schedule of Laboratory Assessments ([Table 4](#)) for the timing and frequency. A central laboratory will perform all clinical laboratory assessments for safety (ie, blood chemistries, hematology assessments, thyroid function, and urinalysis) and will store the samples for [REDACTED] PD. Additional testing may be required by the sponsor based on emerging safety data. All Protocol-required laboratory assessments must be conducted in accordance with the laboratory manual and the Schedule of Laboratory Assessments ([Table 4](#)). Information regarding collection, processing, and shipping of laboratory assessments is provided in the Laboratory Manual.

Clinically significant abnormal laboratory findings are those which are not associated with the underlying disease, unless judged by the investigator to be more severe than expected for the participant's condition. All laboratory tests with values considered clinically significantly abnormal during participation in the study, or within 30 days after the last dose of study treatment, should be repeated until the values return to normal or baseline or are no longer considered clinically significant by the investigator or medical monitor.

See Section 9.1 for information regarding laboratory abnormalities that should be recorded as an AE in the eCRF.

The figure displays a 4x4 grid of 16 8x8 pixel grayscale images, likely representing feature maps from a convolutional neural network. Each image is composed of black and white pixels, showing various patterns such as horizontal and vertical lines, cross-like shapes, and more complex, abstract configurations. The images are arranged in a grid, with each cell containing a different pattern, suggesting a hierarchical or spatially distributed feature space.

